3.0	30 June 2020	Third version due to drug administration update and REC requests (clarified inclusion criterion for ECMO patient cohort, references updated, exploratory laboratory assessment reworded)
4.0	02 March 2021	For detailed list of changes see the Summary of Changes from Protocol v 3.0 to Protocol v 4.0

Clinical Study Code No.: CLI-050000-04	Version No.: 4.0
EUDRACT No.: 2020-002632-75 – IND No: 153286	Date: 02 MAR 2021

PROTOCOL OUTLINE

Study title	Multicenter, open-label, randomised trial to assess the efficacy and tolerability of poractant alfa (porcine surfactant, Curosurf®) in hospitalized patients with SARS-COV-19 acute respiratory distress syndrome (ARDS)
Sponsor	Chiesi Farmaceutici S.p.A. - [name]
Name of the Product	CUROSURF®
Centre(s)	Approximately 7 centers in UK and USA
Indication	ARDS in COVID 19 adult patients
Study design	Multicenter, open-label, randomised, phase II Proof of Concept (POC) study
Study phase	Phase II – Proof of Concept study
Objectives	To evaluate the efficacy and safety of poractant alfa (porcine surfactant, Curosurf®), administered by endotracheal (ET) instillation, in terms of ventilatory free days during the 21 days after randomization, in adult patients with ARDS due to SARS-COV-19 infection.
Treatment duration	Three administrations with a 24 hours dosing interval. Each ET administration 1, 2 and 3 will consist of poractant alfa bolus: 30mg /kg (Lean Body Weight-LBW) = 0.375ml /kg LBW. Dilution with normal saline up to 2ml /kg LBW.
Test product dose/route/regimen	CUROSURF® (poractant alfa) 240mg / 3ml It is a sterile suspension in 3.0 ml glass vials with a total concentration of 80 mg/ml for endotracheal administration. This is a standard natural surfactant prepared from porcine lungs and containing almost exclusively polar lipids, in particular phosphatidylcholine (about 70% of the total phospholipid content), and about 1% of specific low molecular weight hydrophobic proteins SP-B and SP-C.
Reference product dose/route/regimen	NA
Number of patients	Seventy patients will be randomised in the study with a ratio 3:2 (i.e. 42 patients in the poractant alfa arm and 28 in the control arm).
Study population	Adult patients with ARDS due to COVID-19 (positive by rtPCR confirmation) and endotracheally intubated.
Inclusion/exclusion criteria	
Inclusion criteria
 
Participants are eligible to be included in the study if the following criteria apply:
 
 1. Male or female ≥ 18 and ≤ 80 years of age 2. Informed consent for participation in the study (refer to section 15)

Clinical Study Code No.: CLI-050000-04	Version No.: 4.0
EUDRACT No.: 2020-002632-75 – IND No: 153286	Date: 02 MAR 2021

	
for detailed informed consent procedure)
 
 3. Positive 2019-nCoV rt-PCR before randomisation 4. PaO₂/FiO₂ ratio < 150 mmHg 5. Lung compliance ≤45 ml/cmH₂O 6. Intubated and artificially ventilated less than 48 hours before the first poractant alfa administration 
Exclusion criteria
 
Participants are excluded from the study if any of the following criteria apply:
 
 1. Any contraindications to surfactant administration e.g., pulmonary haemorrhage and pneumothorax) 2. Weight < 40kg 3. Stage 4 severe chronic kidney disease (i.e., eGFR < 30) 4. Pregnancy 5. Administration of any nebulized surfactant in the 48 hours before the first poractant alfa administration 6. Extracorporeal membrane oxygenation

Study plan
	
After verification of any inclusion/exclusion criteria the patients will be included in the study and randomised to the poractant alfa group or to standard of care one.
 
Poractant alfa group
 
 - Starting from patient intubation and mechanical ventilation, defined assessments will be collected (for details see study schedule 7.1). - Patients will receive three poractant alfa endotracheal administrations 24 hours apart. - Defined assessments will be collected before randomisation and at 6 -12 - 24 hours after each poractant alfa administration till 72 hours since the first administration. - From Day 4 to Day 27 assessment collection will occur every 24 hours until Intensive Care Unit (ICU) discharge. Whenever the discharge occurs, additional safety lab and SOFA assessments will be collected. - At Day 28 the last follow up evaluation will occur on the ICU if still requiring critical care, or by phone call if the patient has been discharged from ICU by that time. 
Control group
 
 - Starting from patient intubation and mechanical ventilation defined assessments will be collected (for details see study schedule 7.1). - Defined assessments will be collected before randomisation and at specific timepoints (according to study schedule 7.1) from

Clinical Study Code No.: CLI-050000-04	Version No.: 4.0
EUDRACT No.: 2020-002632-75 – IND No: 153286	Date: 02 MAR 2021

	
randomisation up to 72 hours.
 
 - From Day 4 to Day 27 assessment data collection (according to study schedule 7.1) will occur every 24 hours until Intensive Care Unit (ICU) discharge. Whenever discharge occurs, assessment data will be collected at the corresponding Day X. - At Day 28 the last follow up evaluation will occur on the ICU, or by phone call if the patient has already been discharged.
Most relevant allowed concomitant treatments	
Concomitant treatments are allowed.
 
Concomitant medications in a critically ill SARS-COV19 population are numerous may change daily are consequently difficult to collect, and are unlikely, to be related to therapeutic success and or safety evaluations.
 
Therefore, only selected concomitant medications will be specifically recorded in this trial:
 
 1) Antiviral drugs; 2) Monoclonal antibodies; 3) Antibiotics; 4) Systemic corticosteroids; 5) Heparin or any other anticoagulants; 6) Plasma administration from immunized patients; 7) Nitric Oxide therapy; 8) Any other treatments for pneumonia/ARDS/ SARS-COV19 ARDS; 9) Medications prescribed to treat adverse events (AEs).
Most relevant forbidden concomitant treatments	No concomitant treatment is forbidden
Efficacy variables	
Primary Endpoint
 
The primary outcome variable will be the number of days alive and ventilator-free, defined as the number of days the patient is alive and is not receiving mechanical ventilation over the 21 days following randomisation. Mechanical ventilation will be defined as invasive and non-invasive. Patient will be defined free of mechanical ventilation after 12 hours from the suspension of either invasive and non-invasive ventilation. Patients who die or are mechanically ventilated longer than this period are assessed as zero ventilator-free days.
 
Key secondary
 
Percentage of patients alive and free of respiratory failure (i.e., need for mechanical ventilation, ECMO (Extracorporeal Membrane Oxygenation), non-invasive ventilation, or high-flow nasal cannula oxygen delivery) at Day 28.
 
Secondary
 
 - Number of days alive and ventilator-free at Day 28 - Mortality at Day 21 and Day 28

Clinical Study Code No.: CLI-050000-04	Version No.: 4.0
EUDRACT No.: 2020-002632-75 – IND No: 153286	Date: 02 MAR 2021

	
 - Number of alive and free from invasive ventilation at Day 21 and Day 28 - Number of alive and free from non-invasive ventilation (NIV) at Day 21 and Day 28 - Percentage of patients with improvement in severity status defined as a decrease in the severity score at Day 28 or Discharge, whichever comes first. Severity score will be defined as Mild, Moderate, Severe or Death based on PaO₂/FiO₂ ratio and patient status at Day 28 and numerically rated from 1-4 respectively: 
  
 Severity	Variable	Criteria	
   
 Mild -1	PaO₂/FiO₂ Ratio	200 mmHg < PaO₂/FIO₂ ≤ 300 mmHg	
 
 Moderate-2	PaO₂/FiO₂ Ratio	100 mmHg < PaO₂/FIO₂ ≤ 200 mmHg	
 
 Severe-3	PaO₂/FiO₂	Ratio PaO₂/FIO₂ ≤ 100 mmHg	
 
 Death-4	Patient Status	Yes/No	
  
 
 - Change from baseline in PaO₂/FiO₂ ratio at 6 and 12 hours following administration of each dose in the treated group and at similar timepoints in the control group (6, 12, 30, 36, 54 and 60 hours after randomisation) - Change from baseline in PaO₂/FiO₂ ratio at additional timepoints (i.e. every 24 hours after treatment/randomisation until the patient is discharged from the ICU) - Percentage of patients alive and with PaO₂/ FiO₂ improvement >20% at 6 and 12 hours following administration of each dose in the treated group and at similar timepoints in the control group (6, 12, 30, 36, 54 and 60 hours after randomisation) - Percentage of patients alive and with PaO₂/FiO₂ improvement of >20% at the additional timepoints (i.e. every 24 hours after treatment/randomisation until the patient is discharged from the ICU) - Change from baseline in FiO₂ at 6 and 12 hours following administration of each dose in the treated group and at similar timepoints in the control group (6, 12, 30, 36, 54 and 60 hours after randomisation) - Change from baseline in FiO₂ at additional timepoints (i.e. every 24 hours after treatment/randomisation until the patient is discharged from the ICU) - Length of ICU stay (days) at Day 28. Patients who die or are mechanically ventilated longer than this period are assigned with 28 days - Percentage of patients alive and out of ICU at Day 28 	Severity	Variable	Criteria	Mild -1	PaO ₂ /FiO ₂ Ratio	200 mmHg < PaO ₂ /FIO ₂ ≤ 300 mmHg	Moderate-2	PaO ₂ /FiO ₂ Ratio	100 mmHg < PaO ₂ /FIO ₂ ≤ 200 mmHg	Severe-3	PaO ₂ /FiO ₂	Ratio PaO ₂ /FIO ₂ ≤ 100 mmHg	Death-4	Patient Status	Yes/No
Severity	Variable	Criteria														
Mild -1	PaO ₂ /FiO ₂ Ratio	200 mmHg < PaO ₂ /FIO ₂ ≤ 300 mmHg														
Moderate-2	PaO ₂ /FiO ₂ Ratio	100 mmHg < PaO ₂ /FIO ₂ ≤ 200 mmHg														
Severe-3	PaO ₂ /FiO ₂	Ratio PaO ₂ /FIO ₂ ≤ 100 mmHg														
Death-4	Patient Status	Yes/No														

Clinical Study Code No.: CLI-050000-04	Version No.: 4.0
EUDRACT No.: 2020-002632-75 – IND No: 153286	Date: 02 MAR 2021

	
 - Delta SOFA Score and sub-score components measured on Day 3 and Day 28 or Discharge whichever comes first - Percentage of patients alive and organ failure free (SOFA score=0) at Day 28 or Discharge whichever comes first - Change from baseline in ventilatory parameters [tidal volume (TV), respiratory rate (RR), dynamic compliance (C_{dyn}), static compliance (C_{stat}), positive end-expiratory pressure (PEEP), peak inspiratory pressure (PIP), plateau pressure (P_{plat})] measured at 6-12-24h after each poractant alfa administration up to 72 hours and at similar timepoints in the control group (6, 12, 24, 30, 36, 48, 54, 60 and 72 hours after randomisation) and then every 24 hours until the patient is discharged from the ICU - Change from baseline in blood gas analysis acid-base balance parameters (i.e. pH, pCO₂, pO₂, HCO₃, lactate) measured at 6-12-24h after each poractant alfa administration up to 72 hours and at similar timepoints in the control group (6, 12, 24, 30, 36, 48, 54, 60 and 72 hours after randomisation) and then every 24 hours till the patient is discharged from the ICU. 
Exploratory (to be applied only in patients from UK)
 
The following parameters will be measured at 12, 24, 48, 72 and 96 hrs after start of treatment (first dose in the poractant alfa group and after randomisation in the control group):
 
 - Change from baseline in lowest and dynamic surface tensions (mN/m) from TA samples - Change from baseline in concentrations of surfactant phospholipids (mg/ml) and proteins (ng/ml) from TA samples - Change from baseline in inflammatory indices such as cellular and cytokine (pg/ml) inflammatory markers (e.g. IL-1, IL-6, TNF alpha, IFN gamma and lymphocyte markers) from TA and blood samples
Safety variables	
 - Adverse events (AEs) - Laboratory Parameters (Blood count, bilirubin, creatinine, LDH, D-dimer, CRP (C-Reactive Protein), procalcitonin) - Vital Signs (Blood pressures and pulse rate)
Sample size calculation	
A total of 70 patients will be randomised with a ratio 3:2 (i.e. 42 patients randomised to the poractant alfa group and 28 in the control group).
 
Assuming patients in the control arm being free from ventilation on average 1 week (i.e. 7 days), this sample size achieves 84% power to detect a difference of 4 days (i.e. on average 11 ventilation-free days for patients treated with poractant alfa), assuming a standard deviation of 5.5 and a two-sided significance level (alpha) of 0.05 using a two-sample t-test.

Statistical methods	
Populations for analysis
 
 • Intention-to-Treat population (ITT): all randomised patients (analysed as randomised).

Clinical Study Code No.: CLI-050000-04	Version No.: 4.0
EUDRACT No.: 2020-002632-75 – IND No: 153286	Date: 02 MAR 2021

	
 • Safety population: all randomised patients and receive at least one dose of the study treatment (Curosurf treated patients) (analysed as treated). 
The primary analysis population for efficacy will be the ITT. The Safety population will be used in the analysis of all safety variables.
 
Intercurrent Events
 
Death and Early discontinuation from study drug can be anticipated as intercurrent events:
 
 - Death will be incorporated as a failure outcome for binary endpoint using composite strategy; - Early discontinuation from study drug will be handled using treatment policy strategy: all data collected after discontinuation from study drug till Day 28 or death will be included; - Change in respiratory parameters will be analysed using while-alive strategy. 
Primary Efficacy Variable
 
 • Number of days alive and ventilator-free during the 21 days after randomisation will be compared between groups by using the ANOVA model including treatment group, age and country as factors. Patients who die or are mechanically ventilated longer than this period are assessed as zero ventilator-free days. 
Key secondary endpoint
 
 • Percentage of patients alive and free of respiratory failure (i.e., need for mechanical ventilation, ECMO, non-invasive ventilation, or high-flow nasal cannula oxygen delivery) at Day 28 will be analysed using logistic regression including treatment group, age and country as factor. Difference in the proportion and related 95% confidence interval will be estimated from the model. 
Secondary Efficacy Variables
 
 • Number of days alive and free from ventilation at Day 28, number of days alive and free from invasive and non-invasive ventilation at Day 21 and Day 28 will be compared between groups by the ANOVA model including treatment group, age and country as factors. • Mortality at Day 21 and Day 28 will be compared between groups by using logistic regression including treatment group, age and country as factors. Difference in the proportions and related 95% confidence interval will be estimated from the model. • Percentage of patients with improvement in severity status defined as a decrease in the severity score at Day 28 or Discharge, whichever comes first will be compared by groups using logistic regression including treatment group, age and country as factors. Difference in the proportions and related 95% confidence interval will be estimated from the model.
--	--

Clinical Study Code No.: CLI-050000-04	Version No.: 4.0
EUDRACT No.: 2020-002632-75 – IND No: 153286	Date: 02 MAR 2021

	
 • Change from baseline in PaO₂/FiO₂ at 6 and 12 hours after each treatment and at similar timepoints in the control group will be compared between groups using ANCOVA model including group, age and country as fixed effect and baseline value as covariate. The same analysis will be performed at each additional timepoint. • Percentage of patients alive and with PaO₂/FiO₂ improvement of >20% at 6 and 12 hours following administration of each dose in the treated group and at similar timepoints in the control group will be compared by groups using logistic regression including treatment group, age and country as factors. Difference in the proportions and related 95% confidence interval will be estimated from the model. Patients who die are considered as a failure. The same analysis will be performed at each additional timepoint. • Change from baseline in FiO₂ will be analysed as PaO₂/FiO₂. • Length of ICU stay (days) at Day 28 will be compared between groups will be compared between groups by using the ANOVA model including treatment group, age and country as factors. Patients who die or are mechanically ventilated longer than this period are assigned with 28 days. • Percentage of patients alive and out of ICU at Day 28 using logistic regression including treatment group, age and country as factors. Difference in the proportions and related 95% confidence interval will be estimated from the model. • Delta SOFA Score and sub-score components at Day 3 and Day 28 or Discharge, whichever comes first, will be analysed at each timepoint using ANCOVA model including group, age and country as fixed effect and baseline value as covariate. • Percentage of patients alive and free of organ failure (i.e. SOFA score=zero) at Day 28 or Discharge, whichever comes first will be compared by groups using logistic regression including treatment group, age and country as factors. Difference in the proportions and related 95% confidence interval will be estimated from the model. • Change from baseline in ventilator parameters (TV, RR, Cdyn, Cstat, PEEP, PIP, Pplat) will be summarized by means of descriptive statistics or frequency distribution, as appropriate by group at each timepoint. • Change from baseline in BGA acid-base balance parameters (i.e. pH, pCO₂, pO₂, HCO₃, lactate) will be summarized by means of descriptive statistics by group at each timepoint. 
Exploratory Efficacy Variables (to be applied only in patients from UK)
 
 • Exploratory parameters from TA aspirates and blood samples will be summarized both as absolute values and as change from baseline values by treatment group at each timepoint using descriptive statistics. 
Safety Variables

--	---

Clinical Study Code No.: CLI-050000-04	Version No.: 4.0
EUDRACT No.: 2020-002632-75 – IND No: 153286	Date: 02 MAR 2021

	
• Incidence of all the AEs, AEs related to poractant alfa (treated group) (ADRs), serious AEs (SAEs) and AEs leading to death will be summarized by group both in terms of frequency of patients with at least one AE and in terms of the frequency of AEs (number of events).• Vital sign values and their change from baseline will be summarized by group at each timepoint using descriptive statistics.• Laboratory parameters and their change from baseline will be summarized by group at each timepoint using descriptive statistics.
--	--

Clinical Study Code No.: CLI-050000-04	Version No.: 4.0
EUDRACT No.: 2020-002632-75 – IND No: 153286	Date: 02 MAR 2021

LIST OF ABBREVIATIONS AND DEFINITION OF TERMS

ADR	Adverse Drug Reaction
ARDS	Acute Respiratory Distress Syndrome
AE	Adverse Event
ABG	Arterial Blood Gas
ANOVA	Analysis of Variance
BAL	Bronchoalveolar Lavage
Cdyn	Dynamic compliance
CRA	Clinical Research Associate
CRF	Case Report Form
CRP	C-Reactive Protein
CRO	Contract Research Organization
Cstat	Static compliance
FPFV	First Patient First Visit
ET	Endotracheal
vvECMO	Veno Venous-Extracorporeal Membrane Oxygenation
ICH	International Conference on Harmonization
ICU	Intensive Care Unit
ITT	Intention to Treat
LPLV	Last Patient Last Visit
LBW	Lean Body Weight
MedDRA	Medical Dictionary for Regulatory Activities
MV	Mechanical Ventilation
NIV	Non-invasive Ventilation
PEEP	Positive End-Expiratory Pressure
PIP	Peak Inspiratory Pressure
Pplat	Plateau pressure
RR	Respiratory Rate
rtPCR	Real Time Polymerase Chain Reaction
SAE	Serious Adverse Event
SmPC	Summary of Product Characteristics
SOFA	Sequential Organ Failure Assessment
SUSAR	Suspected Unexpected Serious Adverse Reaction
TA	Tracheal Aspirate
TV	Tidal Volume

Clinical Study Code No.: CLI-050000-04	Version No.: 4.0
EUDRACT No.: 2020-002632-75 – IND No: 153286	Date: 02 MAR 2021

CONTENT

GENERAL INFORMATION	2
PROTOCOL OUTLINE	4
LIST OF ABBREVIATIONS AND DEFINITION OF TERMS	12
CONTENT	13
1. INTRODUCTION	15
1.1 BACKGROUND INFORMATION.....	15
1.2 STUDY RATIONALE.....	15
1.3 RISK/BENEFIT ASSESSMENT	17
2. STUDY OBJECTIVES	17
2.1 PRIMARY OBJECTIVE(S).....	17
2.2 SECONDARY OBJECTIVE(S).....	18
2.3 EXPLORATORY OBJECTIVE(S).....	18
3. STUDY DESIGN	18
3.1 STUDY DESIGN	18
3.2 END OF TRIAL DEFINITION.....	19
4. PATIENT SELECTION CRITERIA	19
4.1 PATIENT RECRUITMENT	19

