8. EFFICACY ASSESSMENTS

Primary Endpoint

The primary outcome variable will be the number of days alive and ventilator-free defined as the number of days the patient is alive and not receiving mechanical ventilation over the **21 days** following randomisation.

Mechanical ventilation will be defined as invasive and non-invasive. Patient will be defined free of mechanical ventilation after 12 hours from the suspension of either invasive and non-invasive ventilation. Patients who die or are mechanically ventilated longer than this period are assessed as zero ventilator-free days.

Key secondary endpoint

- Percentage of patients alive and free of respiratory failure (i.e., need for mechanical ventilation, ECMO, non-invasive ventilation, or high-flow nasal cannula oxygen delivery) at **Day 28**

Secondary endpoints

- Number of days alive and ventilator-free at **Day 28**
- Mortality at **Day 21** and **Day 28**
- Number of days alive and free from invasive ventilation at **Day 21** and **Day 28**
- Number of days alive and free from non-invasive ventilation (NIV) at **Day 21** and **Day 28**
- Percentage of patients with improvement in severity status defined as a decrease in the severity score at **Day 28 or Discharge**, whichever comes first. Severity score will be defined as Mild, Moderate, Severe or Death based on PaO₂/FiO₂ ratio and patient status at Day 28 and numerically rated from 1-4 respectively:

Severity	Variable	Criteria
Mild - 1	PaO ₂ /FiO ₂ Ratio	200 mmHg < PaO ₂ /FIO ₂ ≤ 300 mmHg
Moderate - 2	PaO ₂ /FiO ₂ Ratio	100 mmHg < PaO ₂ /FIO ₂ ≤ 200 mmHg
Severe - 3	PaO ₂ /FiO ₂	Ratio PaO ₂ /FIO ₂ ≤ 100 mmHg
Death - 4	Patient Status	Yes/No

- Change from baseline in PaO₂/FiO₂ ratio at **6 and 12 hours following administration of each dose** in the treated group and at the similar timepoints in the control group (6, 12, 30, 36, 54 and 60 hours after randomisation)

Clinical Study Code No.: CLI-050000-04	Version No.: 4.0
EUDRACT No.: 2020-002632-75 – IND No: 153286	Date: 02 MAR 2021

- Change from baseline in PaO₂/FiO₂ ratio at additional timepoints (i.e. every 24 hours after treatment/randomisation until the patient is discharged from the ICU)
- Percentage of patients alive and with PaO₂/FiO₂ improvement of >20% at **6 and 12 hours following administration of each dose** in the treated group and at similar timepoints in the control group (6, 12, 30, 36, 54 and 60 hours after randomisation)

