9.3 Others Secondary Efficacy Variables

9.3.1 Number of Days Alive and Ventilator-free at Day 28

First, within subject with a start date filled in the ventilator support form, subjects with at least 12 hours of suspension of ventilation either invasive or non-invasive ventilation will be flagged. Then duration will be calculated within the flagged subject's subset, as below:

- Ventilator-free days = 28-[MAX (End date of invasive ventilation; End date of non-invasive ventilation)] – Date of randomisation + 1].

Subjects who die or are mechanically ventilated longer than this period are assessed as zero ventilator-free days.

Number of ventilator-free days will be described at Day 28.

9.3.2 Mortality at Day 21 and Day 28

The number and proportion of deaths at Day 21 and Day 28 will be presented for both groups.

9.3.3 Number of Days Alive and Free from invasive and Non-Invasive ventilation at Day 21 and Day 28

For Day 21:

First, subjects with at least 12 hours of suspension of ventilation will be flagged by type (i.e. one flag for Non-Invasive, and one for Invasive). Then duration will be calculated within the flagged subject's subsets, as below:

- Invasive ventilation-free days = 21-(End date of invasive ventilation) – Date of randomisation + 1].
- Non-invasive ventilation-free days = 21-(End date of non-invasive ventilation) – Date of randomisation + 1].

If subject never started a non-invasive ventilation then the value will be set to 21 days.

For Day 28:

First, subjects with at least 12 hours of suspension of ventilation will be flagged by type (i.e. one flag for Non-Invasive, and one for Invasive). Then duration will be calculated within the flagged subject's subsets, as below:

- Invasive ventilation-free days = 28-(End date of invasive ventilation) – Date of randomisation + 1].

- Non-invasive ventilation-free days = 28-(End date of non-invasive ventilation) – Date of randomisation + 1].

If subject never started a non-invasive then the value will be set to 28 days.

Subjects who die or are mechanically ventilated longer than this period are assessed as zero ventilator-free days.

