Table 14.2.3	Summary of Number of Days Alive and Ventilator-free at Day 28 (Intention-To-Treat)	TPT002	
 - Display the number of days alive and Ventilator-free at Day 28. - Remove '95% CI for Mean', 'n geometric', 'Geometric mean' categories. 	Add the footnote: [1] Subjects who die or are mechanically ventilated longer than this period are assessed as zero ventilator-free days. Source: Listing 16.2.6.2-b
Table 14.2.4	Summary of Mortality at Day 21 and Day 28 (Intention-To-Treat)	TPT006	
 - Display the number of death at Day 21 and Day 28. - Do not present 'At Any timepoint' line. 	Source: Listing 16.2.6.2-b

Table Number	Table Title	Template Code	Notes	Footnotes/Source Listing Number
Table 14.2.5	Summary of Number of Days Alive and Free from Invasive Ventilation at Day 21 and Day 28 (Intention-To-Treat)	TPT002	
 - Display the number of days alive and free from invasive ventilation at Day 21 and Day 28 - Remove '95% CI for Mean', 'n geometric', 'Geometric mean' categories. 	Add the footnote: [1] Subjects who die or are mechanically ventilated longer than this period are assessed as zero ventilator-free days. Source: Listing 16.2.6.2-b
Table 14.2.6	Summary of Number of Days Alive and Free from Non-Invasive Ventilation at Day 21 and Day 28 (Intention-To-Treat)	TPT002	
 - Display the number of days alive and free from non-invasive ventilation at Day 21 and Day 28 - Remove '95% CI for Mean', 'n geometric', 'Geometric mean' categories. 	Add the footnote: [1] Subjects who die or are mechanically ventilated longer than this period are assessed as zero ventilator-free days. Source: Listing 16.2.6.2-b

Table Number	Table Title	Template Code	Notes	Footnotes/Source Listing Number

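### SAP 9.3.3 scores NIV-free days on two scales, so a survivor extubated late without NIV outranks one extubated early to short NIV, and no precedence is set for patients still intubated at the end of the window

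*Protocol*

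**What the plan says.** Every patient is on invasive ventilation at entry (Protocol 4.2, inclusion criterion 6). The protocol outline lists "Number of alive and free from non-invasive ventilation (NIV) at Day 21 and Day 28" among the secondary efficacy variables. Section 8 supplies the missing unit: "Number of days alive and free from non-invasive ventilation (NIV) at" Day 21 and Day 28. The outline's statistical methods say that the "number of days alive and free from invasive and non-invasive ventilation at Day 21 and Day 28 will be compared between groups" by ANOVA. The protocol gives no counting rule for this endpoint and does not say how days on the invasive ventilator count.

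SAP 9.3.3 gives three rules.

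- Patients who had NIV: "Non-invasive ventilation-free days = 21-(End date of non-invasive ventilation) – Date of randomisation + 1", followed by a closing bracket whose opening partner is missing.
- Patients who never had NIV: "If subject never started a non-invasive ventilation then the value will be set to 21 days". For the later window: "If subject never started a non-invasive then the value will be set to 28 days".
- At the end of the section: "Subjects who die or are mechanically ventilated longer than this period are assessed as zero ventilator-free days". The footnote to Table 14.2.6 (SAP 16.1), which reports this endpoint at both time points, repeats this.

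SAP 4.1.1 and 9.1 define mechanical ventilation as invasive and non-invasive. SAP 7.5 makes all analyses descriptive, and SAP section 12 lists the formal comparison of NIV-free days among the analyses not done.

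**The concern.** NIV is commonly a step down from the tube, so having had no NIV may mean a clean extubation or a long intubation. The never-started rule treats the two alike and credits the intubated days in full. A patient who steps down to NIV loses every day up to the end of NIV, including the earlier intubated days. The two kinds of patient are thus scored on different scales, and a higher value is not necessarily better.

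Table 14.2.6 will still be produced, next to tables in which a higher value is better. If step-down to NIV is more common in one arm, its mean can point the opposite way to the ventilator-free days, and nothing in the table warns the reader.

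**Working it through.** **Plan's figure.** The documents give no figure for this endpoint. The stated 84% power belongs to the primary comparison (a noncentral t with 68 df gives 83.6%), and nothing below depends on it.

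**Step 1: the formula.** Restoring the lost bracket, the Day 21 score of a patient who had NIV is 21 - [(end of NIV - randomisation) + 1]. By SAP 7.9.3 this is 21 minus the study day on which NIV ended.

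**Step 2: single patients (invented courses), Day 21.**

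| Course | NIV-free days, SAP 9.3.3 | Ventilator-free days |
|---|---|---|
| Intubated to Day 19, no NIV | 21 | 21 - 19 = 2 |
| Extubated Day 5, NIV to Day 10 | 21 - 10 = 11 | 21 - 10 = 11 |
| NIV to Day 6, reintubated to Day 20 | 21 - 6 = 15 | 21 - 20 = 1 |
| Intubated beyond Day 21, no NIV | 21 or 0 | 0 |

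The first patient outranks the second by 10 days here and trails by 9 on ventilator-free days. The zero rule does not alter this, because both are alive and off ventilation before Day 21. The third row shows that invasive days after NIV are credited too. The fourth row is the conflict between rules.

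**Step 3: arm means by hand.** Assumptions: NIV lasts 3 days and nobody dies.

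- Extubation Day 6 (poractant) versus Day 14 (control), NIV in 50% of each arm, nobody intubated at Day 21: 0.5×12 + 0.5×21 = 16.5 versus 0.5×4 + 0.5×21 = 12.5, so +4.0.
- Same extubation days, NIV in 60% versus 20%: 0.6×12 + 0.4×21 = 15.6 versus 0.2×4 + 0.8×21 = 17.6, so -2.0. Ventilator-free days are 0.6×12 + 0.4×15 = 13.2 versus 0.2×4 + 0.8×7 = 6.4, so +6.8.
- Still intubated at Day 21 in 20% versus 40%, the rest extubated Day 10, NIV in 50% of those: extubated patients average 0.5×8 + 0.5×21 = 14.5. If the zero rule prevails: 0.8×14.5 = 11.6 versus 0.6×14.5 = 8.7, so +2.9. If the 21-day rule prevails: 11.6 + 0.2×21 = 15.8 versus 8.7 + 0.4×21 = 17.1, so -1.3.

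**Step 4: simulation.** All inputs are assumed: 35% mortality in both arms scored 0; lognormal extubation day with median 9 (poractant) versus 14 (control) and log-SD 0.6; exponential NIV duration with mean 4 days; 400,000 patients per arm. Differences are poractant minus control at Day 21.

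| NIV use, poractant / control | Ventilator-free days | NIV-free, zero rule prevails | NIV-free, 21-day rule prevails |
|---|---|---|---|
| 50% / 50% | +2.19 | +2.19 | -0.33 |
| 60% / 30% | +1.61 | -0.08 | -2.65 |

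The second row is about +1.7, -0.1 and -2.4 if time is counted continuously instead of in whole days.

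**Step 5: precision.** With a simulated SD of 9 to 10 days and the planned 42 versus 28 patients, the standard error of a difference is SD×√(1/42 + 1/28) = SD×0.244, or 2.2 to 2.4 days. Recruitment stopped short of 70, so the real one would be larger.

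**The case against.** A reader might infer that a patient who stays intubated throughout scores 21 or 28. The documents do not settle that. The zero rule stands in the same section and under the table itself, and on the SAP's definition of mechanical ventilation it gives that patient 0. What the text supports is a conflict without a stated order.

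A reader might also infer that a drug which merely speeds extubation will look harmful. Under the SAP formula with zeros and equal NIV use it looks beneficial, by about as much as on the primary endpoint. With zeros and control NIV use at 30%, the difference still favours poractant at 40% (about +1.5) and at 50% (about +0.7). Reversal needs NIV use to about double, and even then it is slight.

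Nor does the SAP credit intubated days to everyone: for patients who had NIV, those before NIV ended are not counted. The endpoint is no longer tested, and Table 14.2.5 (invasive-ventilation-free days) and Tables 14.2.1 and 14.2.3 (both types combined) give the sound measures. The simulated shifts are within about one standard error, and removing a prespecified endpoint has its own cost.

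All of this limits the point. It does not answer the ranking in Step 2, which holds whichever rule prevails and needs no assumption about NIV rates. That the table is only descriptive does not correct its scoring.

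**Conclusion.** The point holds for how the endpoint is scored. By SAP 9.3.3, late extubation without NIV outranks early extubation to short NIV: 21 against 11 in the example, where ventilator-free days are 2 against 11. For a never-NIV patient still intubated at the end of the window, the rules give 21/28 and 0 with no order between them.

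The effect on the arm comparison is conditional. Under the assumed inputs it is about +2.2 days, in line with the primary endpoint, if the zero rule prevails and NIV use is equal. It is about -0.1 if NIV use is 60% versus 30%. If the 21-day rule prevails it is about -0.3 at equal use and about -2.6 at 60% versus 30%. The documents give no mortality, extubation times or NIV rates for planning, so these figures show direction and rough size only.

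The primary endpoint is untouched. The consequence is one secondary descriptive table that could be misread, which is worth correcting because the correction is cheap.

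**What to change.** In SAP 9.3.3 and Table 14.2.6, delete the rule that sets never-NIV patients to 21 or 28 days, and stop presenting NIV-free days as a measure with a direction of benefit. Summarise days on NIV after extubation by arm instead, with the number extubated. Read benefit from the combined ventilator-free days and the invasive-ventilation-free days. Record the change in SAP section 12, or in the clinical study report if outputs already exist; the SAP introduction provides for explaining departures there.

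If the endpoint is kept as prespecified, the minimum is to state in 9.3.3 that the zero rule takes precedence, and to footnote Table 14.2.6 that never-NIV scores include intubated days, so a higher value is not necessarily better.

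Cost: SAP wording, one revised table shell, and a declared departure from a prespecified secondary endpoint. No new data are needed: Listing 16.2.6.1 already shows ventilator type with start and stop times.
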